#### **6.1.4 Visit 4 (Week 8)**

At least the first session of the infusion cycle will be administered at the site. The following assessments will be performed:

Before the infusion session:

- Patient diary check.
- Physical examination.
- Vital signs.
- Blood sample for safety laboratory (hematology and clinical chemistry). If hemoglobin is found to have decreased by  $\geq 2$  g/dL from baseline, the additional safety laboratory parameters (serum haptoglobin, plasma-free hemoglobin) and Direct Coombs' test will be performed as well.
- Blood sample for serum IgG.
- Blood samples for enzymes.
- CSM.
- CDASI.
- Visit registration in IRT.

During and after the infusion session:

- Administration/Infusion of IMP.
- Vital signs at least once during and 1 hour (+/- 10 min) after the end of the infusion session.

**At least 1 hour after the infusion session:**

- Wells probability score for DVT. If score is likely for DVT ( $\geq 2$  points), perform Doppler scan and take blood sample for D-dimers.
- Wells probability score for PE.
- Assessment of local injection site reactions.

In addition, AEs will be monitored and concomitant therapy will be documented.

**6.1.5 Visit 5 (Week 12)**

At least the first session of the infusion cycle will be administered at the site. The following assessments will be performed:

**Before the infusion session:**

- Patient diary check.
- Physical examination.
- Vital signs (including body weight).
- Blood sample for safety laboratory (hematology and clinical chemistry).
- Blood sample for additional safety lab parameters (serum haptoglobin, plasma-free hemoglobin).
- Direct Coombs' test (if positive, the antibodies responsible for the positive Coombs' test will be eluted to investigate their specificity (anti-A, anti-B or anti-D)).
- Urinalysis.
- Blood sample for serum IgG.
- Blood samples for enzymes.
- Blood sample for biomarkers of disease activity.
- CSM.
- CDASI.
- Visit registration in IRT.

**During and after the infusion session:**

- Administration/Infusion of IMP.
- Vital signs at least once during and 1 hour (+/- 10 min) after the end of the infusion session.

**At least 1 hour after the infusion session:**

- Wells probability score for DVT. If score is likely for DVT ( $\geq 2$  points), perform Doppler scan and take blood sample for D-dimers.
- Wells probability score for PE.
- Assessment of local injection site reactions.

In addition, AEs will be monitored and concomitant therapy will be documented.

### 6.1.6 Visit 6 (Week 16)

At least the first session of the infusion cycle will be administered at the site. The following assessments will be performed:

Before the infusion session:

- Patient diary check.
- Physical examination.
- Vital signs.
- Blood sample for safety laboratory (hematology and clinical chemistry). If hemoglobin is found to have decreased by  $\geq 2$  g/dL from baseline, the additional safety laboratory parameters (serum haptoglobin, plasma-free hemoglobin) and Direct Coombs' test will be performed as well.
- Blood sample for serum IgG.
- Blood samples for enzymes.
- CSM.
- CDASI.
- Visit registration in IRT.

During and after the infusion session:

- Administration/Infusion of IMP.
- Vital signs at least once during and 1 hour (+/- 10 min) after the end of the infusion session.

At least 1 hour after the infusion session:

- Wells probability score for DVT. If score is likely for DVT ( $\geq 2$  points), perform Doppler scan and take blood sample for D-dimers.
- Wells probability score for PE.
- Assessment of local injection site reactions.

In addition, AEs will be monitored and concomitant therapy will be documented.

### 6.1.7 Visit 7 (Week 20)

At least the first session of the infusion cycle will be administered at the site. The following assessments will be performed:

Before the infusion session:

- Patient diary check.
- Physical examination.
- Vital signs.
- Blood sample for safety laboratory (hematology and clinical chemistry). If hemoglobin is found to have decreased by  $\geq 2$  g/dL from baseline, the additional safety laboratory parameters (serum haptoglobin, plasma-free hemoglobin) and Direct Coombs' test will be performed as well.
- Blood sample for serum IgG.
- Blood samples for enzymes.

- CSM.
- CDASI.
- Visit registration in IRT.

During and after the infusion session:

- Administration/Infusion of IMP.
- Vital signs at least once during and 1 hour (+/- 10 min) after the end of the infusion session.

At least 1 hour after the infusion session:

- Wells probability score for DVT. If score is likely for DVT ( $\geq 2$  points), perform Doppler scan and take blood sample for D-dimers.
- Wells probability score for PE.
- Assessment of local injection site reactions.

In addition, AEs will be monitored and concomitant therapy will be documented.

#### **6.1.8 Visit 8 (Week 24)**

At least the first session of the infusion cycle will be administered at the site. The following assessments will be performed:

Before the infusion session:

- Patient diary check.
- Physical examination.
- Vital signs (including body weight).
- Blood sample for safety laboratory (hematology and clinical chemistry).
- Blood sample for additional safety lab parameters (serum haptoglobin, plasma-free hemoglobin).
- Direct Coombs' test (if positive, the antibodies responsible for the positive Coombs' test will be eluted to investigate their specificity (anti-A, anti-B or anti-D)).
- Urinalysis.
- Blood sample for serum IgG.
- Blood samples for enzymes.
- Blood sample for biomarkers of disease activity.
- CSM.
- CDASI.
- Visit registration in IRT.

During and after the infusion session:

- Administration/Infusion of IMP.
- Vital signs at least once during and 1 hour (+/- 10 min) after the end of the infusion session.

At least 1 hour after the infusion session:

- Wells probability score for DVT. If score is likely for DVT ( $\geq 2$  points), perform Doppler scan and take blood sample for D-dimers.
- Wells probability score for PE.
- Assessment of local injection site reactions.

In addition, AEs will be monitored and concomitant therapy will be documented.

**6.1.9 Visit 9 (Week 28)**

At least the first session of the infusion cycle will be administered at the site. The following assessments will be performed:

Before the infusion session:

- Patient diary check.
- Physical examination.
- Vital signs.
- Blood sample for safety laboratory (hematology and clinical chemistry). If hemoglobin is found to have decreased by  $\geq 2$  g/dL from baseline, the additional safety laboratory parameters (serum haptoglobin, plasma-free hemoglobin) and Direct Coombs' test will be performed as well.
- Blood sample for serum IgG.
- Blood samples for enzymes.
- CSM.
- CDASI.
- Visit registration in IRT.

During and after the infusion session:

- Administration/Infusion of IMP.
- Vital signs at least once during and 1 hour (+/- 10 min) after the end of the infusion session.

At least 1 hour after the infusion session:

- Wells probability score for DVT. If score is likely for DVT ( $\geq 2$  points), perform Doppler scan and take blood sample for D-dimers.
- Wells probability score for PE.
- Assessment of local injection site reactions.

In addition, AEs will be monitored and concomitant therapy will be documented.

**6.1.10 Termination Visit (Week 32 or Drop-out Visit)**

The Termination Visit is performed at Week 32.

The following assessments will be performed:

- SF-36v2.
- Patient diary check.

- Physical examination.
- Vital signs and body weight.
- Blood sample for safety laboratory (hematology and clinical chemistry).
- Blood sample for additional safety lab parameters (serum haptoglobin, plasma-free hemoglobin).
- Direct Coombs' test (if positive, the antibodies responsible for the positive Coombs' test will be eluted to investigate their specificity (anti-A, anti-B or anti-D)).
- Urinalysis.
- Blood sample for serum IgG.
- Blood samples for enzymes.
- Blood sample for viral markers.
- Blood sample for biomarkers of disease activity.
- CSM.
- CDASI.
- Wells probability score for DVT. If score is likely for DVT ( $\geq 2$  points), perform Doppler scan and take blood sample for D-dimers.
- Wells probability score for PE.
- Monitoring of AEs.
- Assessment of local injection site reactions.
- Documentation of concomitant therapy.
- Pregnancy test (in WOCBP).
- Visit registration in IRT.

#### **6.1.11 Week 33 Safety Follow-up**

The Safety Follow-up visit is performed at week 33 (1-2 weeks after the last IMP administration). At minimum, all patients should be assessed for:

- Vital signs.
- Wells probability score for DVT. If score is likely for DVT ( $\geq 2$  points), perform Doppler scan and take blood sample for D-dimers.
- Wells probability score for PE.
- Adverse Events.
- Concomitant therapy.

Other safety and/or efficacy laboratory assessments, and physical exam should be repeated only if found abnormal at the termination visit.

After the final examination, the clinical study is considered completed for the subject/patient. No further study-related assessments will be performed, unless safety concerns (e.g., ongoing AEs) require follow-up.

The Investigator will follow up on each AE until it has resolved or until the medical condition of the subject has stabilized. Any relevant follow-up information will be reported to the Sponsor.

### 6.1.12 Time Windows Used in this Study, including Tolerances

In this study, the following time windows and tolerances apply:

**Table 5: Time Windows Used in This Study**

Time Point	Time stated	Tolerance
Interval between visits	4 weeks	± 4 days
Interval between infusion cycles	1 week	± 2 days
Interval between infusion sessions	Same day or on two consecutive days or with maximum one day in between two sessions	1 – 54 hours
Vital signs	before IMP administration at the site 1 hour after the infusion session	≤ 60 minutes ± 10 minutes
Direct Coombs' test	before IMP administration at the site	≤ 4 hours
Wells probability score for DVT	after IMP administration at the site	≥ 60 minutes
Wells probability score for PE	after IMP administration at the site	≥ 60 minutes

## 6.2 Duration of the Study

### 6.2.1 Planned Duration for an Individual Subject/Patient

The duration of the entire study for each subject will be up to 35 weeks and consists of the following segments: up to 2 weeks for Screening, then 32 weeks of double-blind treatment period, followed by a 1 week safety follow-up period.

For patients from GAM10-08 study, GAM10-08 Week 40 Termination Visit will be SCGAM-02 Baseline Visit.

### 6.2.2 Planned Duration for the Study as a Whole

The study will be considered completed when all subjects have completed the planned observation period/Final Examination Visit.

The study as a whole should be completed within about 24 months. The estimated clinical start of the study (enrolment of first subject) is Q3 2018 with the estimated clinical end in Q2 2020.

The clinical end of the study is defined as the last visit of the last subject participating in the study.

The clock start date for results publication is the date of database lock of the clinical study database when all data cleaning activities have been completed.

### 6.2.3 Premature Termination of the Study

Both the Investigator and the Sponsor reserve the right to terminate the study at any time. In this event, any necessary procedures will be arranged on an individual study basis after review and consultation by both parties. In terminating the study, the Sponsor and the Investigator will ensure that adequate consideration is given to the protection of the patients' interests.

Regulatory authorities and IECs/IRBs should be informed in accordance with national regulations.

Early termination of the study as a whole or by centre may apply for the following reasons:

#### 6.2.3.1 Early Termination of the Entire Clinical Study

At any time, the study as a whole will be terminated prematurely if:

- New toxicological or pharmacological findings or safety reports invalidate the earlier positive benefit-risk-assessment.
- If more than 3 TEEs (i.e. ischemic stroke, transient ischemic attack, cerebral infarction, cerebrovascular accident, cerebral thrombosis, embolic infarctions, [acute] myocardial infarction, deep vein thrombosis, pulmonary embolism, venous thrombosis excluding thrombophlebitis or infusion site thrombosis) are observed during the treatment period of the study, fulfilling the following criteria:
  - assessed as probably or possibly related to *octanorm* 16.5% treatment by Investigator and/or Sponsor;
  - confirmed by the Independent Data Monitoring Committee (IDMC);

**AND**

if  $\leq 2$  TEEs (as defined above) are observed during the treatment period of the study, fulfilling the following criteria:

- assessed as probably or possibly related to placebo treatment by Investigator and/or Sponsor;
- confirmed by the IDMC.

*NOTE: Causality assessments of suspected TEEs have to be made in a blinded manner by all involved parties (Investigator, Sponsor, IDMC). After individual causality assessment, the IDMC is entitled to unblind cases in order to monitor the stopping rule.*

- If more than 4 clinically significant (definition see **Section 7.3.2.1**) hemolytic transfusion reactions (HTRs) are observed during the treatment period of the study, fulfilling the following criteria:
  - assessed as probably or possibly related to *octanorm 16.5%* treatment by Investigator and/or Sponsor;
  - confirmed by the IDMC.

**AND**

if less than 3 clinically significant HTRs are observed during the treatment period of the study, fulfilling the following criteria:

- assessed as probably or possibly related to placebo treatment by Investigator and/or Sponsor;
- confirmed by the IDMC.

*NOTE: Causality assessments of suspected HTRs have to be made in a blinded manner by all involved parties (Investigator, Sponsor, IDMC). After individual causality assessment, the IDMC is entitled to unblind cases in order to monitor the stopping rule.*

- Any other reason rendering the continuation of the study impossible for the Sponsor.

#### **6.2.3.2 Early Termination at an Individual Study Centre**

At any time, the study can be terminated at an individual centre if:

- The centre cannot comply with the requirements of the protocol.
- The centre cannot comply with GCP standards.
- The centre's first patient is not recruited by 20 weeks after initiation of the centre.
- The required recruitment rate is not met.

Should the study be prematurely terminated, all study materials (IMPs, etc.) must be returned to the Sponsor.

## 7 ASSESSMENTS AND METHODS

### 7.1 Demographic and Baseline Information

The following information will be recorded during the Screening Visit:

#### 7.1.1 Demographic and Baseline Characteristics

The demographic and baseline characteristics are sex, age, race, ethnic origin, height, weight, and Body Mass Index (BMI).

#### 7.1.2 Medical History and Prior/Concomitant Medications

The medical history will be obtained by interviewing the subject/patient. Records of past diseases and treatments (e.g., hospital discharge letters) will be obtained for the study files, if available. Based on the available data patients will also be classified according to The European League Against Rheumatism/American College of Rheumatology (EULAR/ACR) classification criteria for adult and juvenile idiopathic inflammatory myopathies (IIMs).

Prior and concomitant medications as well as physical therapy-directed exercise regimen will be obtained by interview.

For patients from GAM10-08 study: Information on medical history and on prior and concomitant therapy can be taken from GAM10-08 study records.

### 7.2 Efficacy Assessments

CSM assessments should always be performed by the same investigator or designee. The same applies to the assessment of CDASI. Training for CSM and CDASI will be done by third parties.

6 CSM of myositis disease activity have been established for clinical trials in subjects with DM and PM:

- Physician's Global Disease Activity (part of MDAAT; 10 cm VAS assessing global disease activity from "No evidence of disease activity" to "Extremely active or severe disease activity"; Disease Activity being defined as potentially reversible pathology or physiology resulting from the myositis).
- Patient's Global Disease Activity (10cm VAS assessing the overall activity of the patient's disease today from "No evidence of disease activity" to "Extremely active or severe disease activity", Disease Activity being active inflammation in the patient's muscles, skin, joints, intestines, heart, lungs or other parts of the body, which can improve when treated with medicines).
- Manual Muscle Testing (MMT-8; a set of 8 designated muscles tested bilaterally [potential score 0 – 150]).
- Health Assessment Questionnaire (HAQ; a generic rather than a disease-specific instrument; comprised of 8 sections: dressing, arising, eating, walking, hygiene, reach, grip, and activities. There are 2 or 3 questions for each section. Scoring within each section is from 0 [without any difficulty] to 3 [unable to do]. For each section the score given to that section is the worst score within the section. The 8 scores of the 8 sections are summed and divided by 8).[38, 39]

- Enzymes (aldolase, creatine kinase, alanine aminotransferase [ALAT], aspartate aminotransferase [ASAT], lactate dehydrogenase [LDH]).
- Extra-muscular activity (part of MDAAT; a combined tool that captures the physician's assessment of disease activity of various organ systems using [1] a scale from 0 = "Not present in the last 4 weeks" to 4 = "New - in the last 4 weeks [compared to the previous 4 weeks]" and [2] a VAS).

The CDASI is a clinician-scored single page instrument that separately measures activity and damage in the skin of DM patients for use in clinical practice or clinical/therapeutic studies. The modified CDASI (version 2) is the one in current use. The modified CDASI has 3 activity measures (erythema, scale, and erosion/ulceration) and 2 damage measures (poikiloderma and calcinosis) which are assessed over 15 body areas. In addition, Gottron's papules on the hands are evaluated both for activity and damage. Lastly, the activity of periungual changes and alopecia is assessed.[32]

### **7.2.1 Assessments for Primary Efficacy Endpoint(s)**

"Clinically important deterioration" is defined as follows: 1) MMT-8 worsening  $\geq 6$  points (scale of 150) OR CDASI (Total Activity Score) worsening  $\geq 5$  points, AND 2) Physician's Global Disease Activity VAS worsening  $\geq 2$  cm.

### **7.2.2 Assessments for Secondary Efficacy Endpoint(s)**

The CSM were validated by the International Myositis Assessment and Clinical Studies Group (IMACS). However, conjoint analysis was introduced to develop a definition of improvement derived from the 6 CSM to calculate the TIS. The TIS is a scale from 0 to 100 that allows for the discrimination between minimal, moderate and major responders depending on their improvement in the combined 6 CSM:  $\geq 20$  to 39 points being minimal improvement,  $\geq 40$  to 59 points being moderate improvement, and  $\geq 60$  points being major improvement.[37] It does not discriminate stable from worsening patients.

The Quality of Life questionnaire SF-36 is described in **Section 7.4.3**.

## **7.3 Safety Assessments**

### **7.3.1 Assessments for Safety Endpoints**

Any of the following drug safety information shall be collected:

- Adverse events (AEs) and serious adverse events (SAEs) temporally associated with the administration of IMP, comparator, or placebo (for definitions and reporting requirements, see **Sections 7.3.2**, through **Section 7.3.5**)
- Pregnancies, drug overdose, interaction, medication error, and post-study SAEs (see **Section 7.3.9**)

### 7.3.2 Adverse Events (AEs)

#### 7.3.2.1 Definitions

- **Adverse event (AE):** An AE is any untoward medical occurrence in a study subject/patient receiving an IMP and which does not necessarily have a causal relationship with this treatment. An AE can therefore be any unfavourable and unintended sign (including an abnormal laboratory finding), symptom, or disease temporally associated with the use of an IMP, whether or not related to the IMP.
- **Adverse drug reaction (ADR):** An ADR is any noxious and unintended response to an IMP related to any dose. The phrase 'response to an IMP' means that a causal relationship between the IMP and an AE carries at least a reasonable possibility, i.e., the relationship cannot be ruled out.
- **Other significant AEs:** Any marked laboratory abnormalities or any AEs that lead to an intervention, including withdrawal of drug treatment, dose reduction, or significant additional concomitant therapy.
- **Withdrawal due to AE/ADR:** AE/ADR leading to discontinuation of treatment with IMP. Any such events will be followed up by the Investigator until the event is resolved or until the medical condition of the subject/patient is stable. All follow-up information collected will be made available to the Sponsor.

#### 7.3.2.2 Collection of AEs

The condition of the subject/patient will be monitored throughout the study. At each visit, whether scheduled or unscheduled, AEs will be elicited using a standard non-leading question such as "How have you been since the last visit/during the previous study period?" AEs should be registered starting from the first dose of IMP (start of first injection).

In addition, the Investigator will check the subject/patient diaries (if applicable) for any documented event.

Local injection site reactions are to be assessed by both patients and investigators.

Patients have to grade the overall perception of local reactions in their diaries at 24 hours ( $\pm 3$  hours) post-infusion session using a 4-point rating scale: 0=none, 1=mild, 2=moderate, 3=severe.

Investigators have to evaluate local reactions at approximately 1 hour post-infusion session at every study site visit, using the same 4-point rating scale: 0=none, 1=mild, 2=moderate, 3=severe.

Local infusion site reactions will be noted on the adverse event pages in the CRF.

Any AE or ADR occurring during the study will be noted in detail on the appropriate pages of the eCRF. If the subject reports several signs or symptoms representing a single syndrome or diagnosis, the diagnosis should be recorded in the eCRF. The Investigator will grade the severity of all AEs or ADRs (mild, moderate, or severe), the seriousness (non-serious or serious), and the causality as defined in **Sections 7.3.2.3, 7.3.2.4, and 7.3.3**. The Sponsor is responsible for assessing the expectedness of each ADR (expected or unexpected) as defined in **Section 7.3.2.5**.

In the event of clinically significant abnormal laboratory findings, the tests will be confirmed and the patient followed up until the laboratory values have returned to normal and/or an adequate explanation for the abnormality has become available.

Diseases, signs and symptoms, and/or laboratory abnormalities already present before the first administration of IMP will not be considered AEs unless an exacerbation in intensity or frequency (worsening) occurs.

The Investigator will provide detailed information about any abnormalities and about the nature of and reasons for any action taken as well as any other observations or comments that may be useful for the interpretation and understanding of an AE or ADR.

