In case of clinically important deterioration during the treatment period, subjects will be discontinued from the study, will undergo a termination visit and may optionally receive Octagam 10% as IGIV rescue medication (2g/kg BW one time, provided by the sponsor) or rescue treatment according to standard of care at the site by the treating physician. Octagam 10% or any other commercially available IGIV as optional IGIV rescue medication can be also reimbursed by the sponsor (2g/kg BW one time). IGIV as rescue medication should be administered with infusion rate not higher than 0.04 mL/kg/min (240 mg/kg/h).

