### 9.1 Determination of Sample Size

The sample size calculation is based on the target parameter for the evaluation of the primary endpoint, i.e. the proportions of patients with clinically important deterioration in the active treatment arm (*octanorm*, 0.5 g/kg/week) and the Placebo arm until the end of the 32 week treatment period.

Patients who drop out prematurely or receive rescue treatment for any safety reason or lack of efficacy will also be analysed as patients with clinically important deterioration.

The following assumptions for the true proportion of patients to be analysed as patients with clinically important deterioration, which will include all dropouts, were chosen for the sample size calculation after thorough discussion with Steering Committee members involved in the treatment of DM patients:

- Octanorm arm: 27% (this corresponds to a failure rate of 18.89% in patients randomised to octanorm who completed the study per protocol plus a 10% drop-out rate)
- Placebo arm: 58% (this corresponds to a failure rate of 53.33% in patients randomised to Placebo who completed the study per protocol plus a 10% drop-out rate)

The pair of hypotheses to be tested is:  $H_0: P_O = P_P$  vs.  $H_A: P_O \neq P_P$

where  $P_O$  and  $P_P$  denote the proportions of patients with clinically important deterioration in the *octanorm* and Placebo arm respectively.

With these assumptions, a sample size of 39 patients per treatment arm will be needed to achieve a power of 80% to detect a difference between the group proportions, using the Pearson Chi-square Test for Proportion Difference at a significance level of  $\alpha=0.05$ . It is therefore planned to enrol a minimum of 78 patients, randomized to the two treatments groups in a balanced 1:1 ratio.

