### 9.2 Statistical Test Procedure

To test the null hypothesis  $H_0$  against the alternative hypothesis  $H_A$  a two-sided Pearson Chi-square Test for Proportion Difference will be performed at a significance level of 5% to compare the placebo group against the high dose group.

If a subject is prematurely withdrawn from the study, or misses data required for the evaluation of the primary endpoint, this subject will be analysed as a treatment failure, i.e. as having a clinically important deterioration.

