11.1. Adverse Events

All reported AEs will be coded according to MedDRA.

An AE is defined as treatment-emergent, if first onset or worsening is during the treatment period. Only treatment-emergent AEs (TEAEs) are accounted for in the analysis.

For each TEAE, the exact time of onset will be recorded. A TEAE will be classified as infusional AE if the onset is during the first infusion session of a given infusion cycle, between the two infusion sessions of the same cycle, or within 72 hours after the end of the 2nd infusion session of the same infusion cycle.

All reported events will be listed and tabulated in full detail; in particular the following key figures will be presented:

- Total incidence and number of TEAEs reported by severity and overall
- Incidence and number of related TEAEs by severity and overall
- Incidence and number of TEEs and HTRs
- Incidence and number of SAEs
- Incidence and number of TEAEs leading to withdrawal
- Incidence and number of infusional AEs by severity and overall
- Number of infusion cycles with infusional AEs

Narratives will be prepared describing each death, other SAEs, and other significant AEs that are judged to be of special interest because of clinical importance, including all TEEs and HTRs reported.

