11.6. Further Safety Evaluations

11.6.1. Physical Examination

A general physical examination will be performed at the screening and baseline visit and all relevant abnormalities will be documented. The physical examination will be repeated at each study visit, including the termination visit (irrespective of whether termination is regular or premature), and any clinically relevant worsening from the status at screening will be documented as an AE.

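### SAP 11.1 compares adverse events on crude counts although deterioration ends follow-up unequally, and the plan leaves open whether the deterioration itself is counted as an adverse event

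*Protocol*

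**What the plan says.** **What counts as an AE.** Protocol 7.3.2.1 defines an AE as any untoward occurrence, related or not. Protocol 7.3.2.2 says that diseases and signs present before the first dose "will not be considered AEs unless an exacerbation in intensity or frequency (worsening) occurs". SAP 11.6.1 adds, for the physical examination, that "any clinically relevant worsening from the status at screening will be documented as an AE". Neither document exempts worsening dermatomyositis.

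**What deterioration does to follow-up.** Protocol 4.3.1: "In case of clinically important deterioration during the treatment period, subjects will be discontinued from the study". A termination visit follows. SAP 8.4 runs the treatment period to the end of observation, usually the termination visit at Week 32 or earlier. SAP 11.1 counts only TEAEs with onset or worsening in that period.

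**What is tabulated.** The SAP 11.1 key figures are incidences and numbers, among them "Incidence and number of TEAEs leading to withdrawal". No rate per cycle or per unit of time is specified, and no total without disease worsening.

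**What points the other way.** Protocol 4.3.1 mentions AEs as grounds for withdrawal and lists deterioration of dermatomyositis separately among other reasons. SAP 4.1 regards patients discontinued for deterioration as completers, because they reached the primary endpoint.

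**The concern.** Safety and tolerability is a stated secondary objective. Two features of the plan tie the AE comparison to the efficacy result.

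First, if octanorm works as assumed, more placebo patients leave early. A crude count or incidence then compares arms watched for different lengths of time, and octanorm looks worse on events that occur at the same rate in both arms.

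Second, the general AE rules cover a worsening of dermatomyositis, and Protocol 7.3.2.1 defines withdrawal due to an AE as an AE that leads to discontinuation of study drug. Read together, a deterioration can enter both the any-TEAE count and the TEAE-withdrawal count. Other sections keep it apart from AEs. Where sites do record it, these two counts look worse for placebo because of efficacy, not harm. The two effects have opposite signs, and the plan does not let a reader tell how much of either is present.

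**Working it through.** **1. Reproduce the plan's figures (Protocol 9.1, SAP 6).** The octanorm assumption is explained thus: "this corresponds to a failure rate of 18.89% in patients randomised to octanorm who completed the study per protocol plus a 10% drop-out rate". For placebo: "this corresponds to a failure rate of 53.33% in patients randomised to Placebo who completed the study per protocol plus a 10% drop-out rate".

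- Octanorm: 0.9 × 18.89% + 10% = 27.0%
- Placebo: 0.9 × 53.33% + 10% = 58.0%

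The Pearson chi-square sample size at two-sided α = 0.05 and 80% power, with pooled variance and p̄ = 0.425, is

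n = [1.960 × √(2 × 0.425 × 0.575) + 0.842 × √(0.58 × 0.42 + 0.27 × 0.73)]² / 0.31² = 38.7, rounded up to 39.

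Power at 39 per arm is 80.3%. This agrees with the protocol: "a sample size of 39 patients per treatment arm will be needed to achieve a power of 80% to detect a difference". The rates used below are therefore the plan's own.

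**2. Unequal observation.** Let f be the failure proportion (0.27 or 0.58), with every failure taken as an exit. The documents give no exit times, so these are assumed:

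- all exits at week t: mean weeks = f·t + (1 − f)·32
- uniform exits: mean weeks = 32·(1 − f/2)
- constant hazard: λ = −ln(1 − f)/32 and mean weeks = f/λ

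| Assumed exits | Octanorm, weeks | Placebo, weeks | Octanorm/placebo |
|---|---|---|---|
| Week 8 | 25.5 | 18.1 | 1.41 |
| Constant hazard | 27.5 | 21.4 | 1.28 |
| Uniform | 27.7 | 22.7 | 1.22 |
| Week 24 | 29.8 | 27.4 | 1.09 |

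At equal weekly rates the ratio of event counts equals the ratio of exposure, so octanorm shows 9% to 41% more events. Under constant hazard, 39 patients per arm give 39 × 27.5/52 = 20.6 and 39 × 21.4/52 = 16.0 patient-years. A deterioration first found at Week 32 truncates nothing, so the excess shrinks towards zero as exits get later.

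**3. Deterioration recorded as an AE.** Deteriorations under the definition, as a share of randomised patients:

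- Placebo: 0.9 × 53.33% = 48.0%, or 18.7 of 39
- Octanorm: 0.9 × 18.89% = 17.0%, or 6.6 of 39

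If sites record all of them, they contribute 48% against 17% to the TEAE-withdrawal figure, a gap of 31 points or about 12 patients. If sites record none, the contribution is zero.

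**4. Both effects together (illustration).** Assume that another TEAE has a true 32-week risk of 30% in both arms, so h = −ln(0.7)/32, and that exits follow the constant hazard λ above.

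- Crude incidence without deterioration, h/(h + λ) × (1 − exp(−32(h + λ))): 26.0% octanorm, 20.6% placebo, ratio 1.26.
- Counting every deterioration as well, with h in the numerator replaced by h + λ·c/f, where c is 0.17 or 0.48: 40.4% octanorm, 62.0% placebo, ratio 0.65.

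For assumed true risks of 10% to 70% the first ratio runs from 1.28 to 1.22 and the second from 0.47 to 0.89. With identical underlying risk, the apparent direction depends on a recording practice that the plan does not fix.

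**5. Which figures are affected.** Any-TEAE and TEAE-withdrawal counts can take both effects. SAEs take the second only where a deterioration meets a seriousness criterion (Protocol 7.3.3). Related TEAEs, thromboembolic events (TEEs), hemolytic transfusion reactions (HTRs) and local reactions are affected mainly by shorter observation.

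**The case against.** The strongest reply is that recording deterioration as an AE is an inference. No sentence says that it happens. Protocol 4.3.1 lists it apart from AEs, SAP 4.1 calls these patients completers, and SAP 11.6.1 concerns the general physical examination, whereas the endpoint is scored on MMT-8, CDASI and a global VAS. This stands: 48% against 17% is an upper bound, not a forecast. It does not remove the point, because Protocol 7.3.2.1 and 7.3.2.2 still cover the event and sites could reasonably differ.

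The second reply is that much can be read from planned output. AEs are shown by preferred term, related events separately, withdrawals by reason, local reactions by treatment week, and numbers of infusions under compliance (SAP 9.4). That is partly right. The ingredients of a per-cycle rate are planned, but the rate is not, and no total excludes the disease. The table list is deferred (SAP 13), so such tables could still be added, but nothing now commits to them.

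The third reply is that follow-up does not stop dead. A safety visit takes place 1 to 2 weeks after the last dose (Protocol 6.1.11), and SAEs up to 4 weeks after it are reported if the investigator learns of them (Protocol 7.3.9). SAP 8.3 also defines TEAEs without an end date, unlike SAP 11.1. This softens the truncation slightly; it does not restore the missing weeks.

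A reader might go further and infer that SAE counts would largely restate the primary endpoint, or that the safety conclusion would come out with the wrong sign. The documents support neither. They give no rate of serious deterioration, and the safety analysis is descriptive, with no test or rule that rests a conclusion on crude any-TEAE incidence.

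**Conclusion.** The point holds as a reporting weakness in SAP 11.1. The firmer part is unequal observation: given the assumed 58% and 27% failure rates and discontinuation at deterioration, equal weekly AE rates would produce about 9% to 41% more events on octanorm, and about 28% more under constant hazard. This rests on assumed exit times and on treating every failure as an exit.

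The second part is an ambiguity. Depending on site practice, the efficacy event could add anything from 0 to 31 points to the placebo-minus-octanorm difference in TEAE withdrawals, and it could inflate any-TEAE incidence in the same direction. It should not be read as distorting every safety figure in both directions.

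The primary analysis is untouched. The weight is moderate: safety is descriptive and the table list is open, but the remedy is cheap and is best specified before unblinding.

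**What to change.** In SAP 11.1:

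- Beside each crude incidence and number, give rates per infusion cycle and per patient-week of observation, including for TEEs, HTRs and local reactions. State one end of the TEAE window, so that SAP 8.3, 8.4 and 11.1 agree and numerator and denominator cover the same time.
- Present total TEAEs, SAEs and TEAEs leading to withdrawal twice: all events, and without events that are the dermatomyositis deterioration itself. Flag those events blind at the data review meeting already described in SAP 7. The version without them does not depend on whether a site recorded the deterioration.
- State that the between-arm comparison of AE frequency rests on the exposure-adjusted figures, with both versions of the totals shown.

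AE collection and reporting stay as they are. The data needed (AE onset, infusion records, visit dates) are already collected. The cost is some SAP wording and a few more safety tables.
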